#### Data variables:

The twitch monitoring results in the operating room just prior to reversal, following reversal and hourly in the intensive care unit will be recorded, along with sugammadex doses. The total dose of rocuronium or vecuronium and the time period of neuromuscular blocking drug administration will also be recorded. Data will either be recorded in real time by study assistants or retrieved from the electronic medical record. Data variables: date of procedure, sex, age, weight, height, neuromuscular blocking drug data (dose and time), sugammadex dosing data (dose and time) and twitch monitoring data (prior to, during and after sugammadex administration).

#### Consent process:

An investigator or research assistant will approach subjects on the day of the procedure, but before any sedation by the anesthesia providers in the pre-operative area. The consent information will be discussed in a private room with heavy curtains and with only the subject and principal investigator present. There is minimal risk of auditory privacy loss since the rooms are large and the curtains provide an auditory barrier. These rooms are routinely used by operating room providers (proceduralists, anesthesiologists, and nursing staff) to obtain consent and interview patients about their medical history. The subjects will hear a presentation of the study that will be supported by photos of twitch monitoring equipment. The subjects will have an opportunity to ask questions. The subjects will understand that they will undergo reversal of neuromuscular blockade and twitch monitoring routinely whether or not they participate in the study. If they participate in the study they will additionally undergo titration of sugammadex and additional twitch monitoring in the ICU for up to 6 hours. After the risks and benefits of participation in this study are explained in layman's language, the subject will be asked if he/she has any questions or concerns about participating in the study. The point will be

clearly made that this is a voluntary study and that the subjects have the opportunity for not participating. A paper copy of the signed consent form will be provided to subjects for their records.

#### Anticipated risks:

The risks that are specific to this research are minimal (excluding the risk of anesthesia and cardiac surgery, which are not specific to this research). Patients will receive sugammadex regardless of their participation in this study. By participating in this study, patients may receive a smaller dose of sugammadex than they would otherwise receive. Hypothetically, there may be a small chance that a smaller dose of sugammadex could result in a recurrence of neuromuscular blockade. This is mitigated by the fact that the patients will be intubated and ventilated postoperatively, which is routine care following cardiac surgery, thus any recurrence of neuromuscular blockade would not be harmful. If there is any recurrence of neuromuscular blockade, this will be detected by twitch monitoring and additional sugammadex will be administered. The patients participating in this study will not be under anesthesia in the operating room or intensive care unit for a longer time than patients not participating in this study.

#### Data and safety monitoring:

The PI reviews serious adverse events in real time. The PI will monitor the study and ensure that protocol deviations, AEs, and SAEs are reported to the IRB according to HSD and IRB reporting requirements. For this study, the following standard AE definitions are used:

**Adverse event:** Any event that requires administration of sugammadex after the patient leaves the operating room, prior to extubation.

**Not related:** The AE is clearly not related to the study procedures (i.e., another cause of the event is most plausible and/or a clinically plausible temporal sequence is inconsistent with the onset of the event).

**Possibly related:** An event that follows a reasonable temporal sequence from the initiation of study procedures,

but that could readily have been produced by a number of other factors.

**Related:** The AE is clearly related to the study procedures.

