**Study design:**

Cardiac surgery patients will receive sugammadex in 50 mg increments at the end of surgery, until the train-of-four ratio is at least 0.9 and the train-of-four ratio will be measured hourly in the ICU for 6 hours or until extubation, whichever comes first.

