**Exclusion criteria:**

Allergy or other contraindication to the use of sugammadex

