#### Study procedures:

1. Standard clinical procedure for monitoring and reversal of neuromuscular blockade—Neuromuscular blockade is monitored with EMG-based quantitative twitch monitoring (TwitchView). At the end of surgery, sugammadex is administered to reverse neuromuscular blockade, as defined by a train-of-four ratio of 0.9 or greater. The patient is transported asleep, intubated and ventilated to the intensive care unit where the train-of-four ratio of 0.9 or greater is confirmed on arrival by the respiratory therapist.
2. Study procedure—Instead of administering a standard dose of sugammadex 2 mg/kg or 4 mg/kg, sugammadex will be titrated in 50 mg increments every 5 minutes until a train-of-four ratio of 0.9 or greater is reached. Train-of-four ratio will be measured on arrival in the intensive care unit and then hourly for 6 hours or until extubation if extubation occurs in <6 hours. If the train-of-four ratio is less than 0.9 at any time, additional sugammadex will be administered until the train-of-four ratio is 0.9 or greater. The twitch monitoring results in the operating room just prior to reversal, following reversal and hourly in the intensive care unit will be recorded, along with sugammadex doses. The total dose of rocuronium or vecuronium and the time period of neuromuscular blocking drug will also be recorded. Data will either be recorded in real time by study assistants or retrieved from the electronic medical record. The patient's age, gender, and weight will be recorded. Data will be obtained by study assistants or from the electronic medical record.

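### The adverse event definition covers only sugammadex given between leaving the operating room and extubation, so a non-serious titration reaction, or recurrent weakness or reintubation after extubation, is not an adverse event

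*Combined protocol and SAP*

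**What the plan says.** All references are to the combined protocol and SAP.

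- **Data and safety monitoring** announces that "the following standard AE definitions are used" and gives one definition of an adverse event: "Any event that requires administration of sugammadex after the patient leaves the operating room, prior to extubation". The three entries that follow (not related, possibly related, related) grade causality and do not widen it. The PI is to review serious adverse events as they occur and to ensure that protocol deviations, "AEs, and SAEs are reported to the IRB according to HSD and IRB reporting requirements". Seriousness is not defined.
- **Study design** places the titration before the ICU stay: "Cardiac surgery patients will receive sugammadex in 50 mg increments at the end of surgery".
- **Study procedures** agrees: "The twitch monitoring results in the operating room just prior to reversal, following reversal and hourly in the intensive care unit will be recorded". The ratio is then "measured on arrival in the intensive care unit and then hourly for 6 hours or until extubation", and more sugammadex is given whenever it is found below 0.9.
- **Exclusion criteria** has one entry: "Allergy or other contraindication to the use of sugammadex".
- **Anticipated risks** names recurrence of blockade after a smaller dose as the hypothetical risk of taking part. It regards recurrence as harmless because the patient is still intubated and on the ventilator, and adds that twitch monitoring would detect it.
- **Data variables** lists demographics, relaxant and sugammadex doses with times, and twitch data. It lists no reaction, weakness or reintubation.

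**The concern.** The definition sets two conditions: the event must call for sugammadex, and it must fall between leaving the operating room and extubation. Both the study drug's planned use and the period of least protection lie outside that window.

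A reader who sees a statement that no adverse events occurred, under definitions called standard, would take it to cover drug reactions and breathing problems after the tube is removed. Under this definition it covers neither. What it does capture, re-dosing in the ICU, is triggered by a ratio below 0.9. That nearly coincides with failure of the study hypothesis in Objectives, so the adverse event count adds little safety information beyond the study's own outcome.

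**Working it through.** No arithmetic applies, and there is no figure in the plan to reproduce: Statistical analysis gives no numerical sample size and plans no adverse event analysis. The check is to apply the two conditions in the definition to each kind of event.

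| Event | Calls for sugammadex? | Between leaving the operating room and extubation? | Adverse event as written? |
|---|---|---|---|
| Ratio below 0.9 in the ICU before extubation, sugammadex given | Yes | Yes | Yes |
| Reaction to an increment during titration in the operating room | No | No, too early | No |
| Recurrent weakness after extubation | Possibly | No, too late | No |
| Reintubation after extubation | Not necessarily | No, too late | No |

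**Titration.** Study design and Study procedures together put the planned increments in the operating room, before the window opens. A reaction there fails both conditions. The protocol recognises such a hazard, since its only exclusion is sugammadex allergy or another contraindication. Data and safety monitoring is also inconsistent within itself. The possibly-related grade runs its time sequence from the start of study procedures, which begin in the operating room, yet an event there cannot qualify to be graded.

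**After extubation.** Anticipated risks relies on two safeguards against recurrence. The first, the tube and ventilator, ends at extubation. The second, scheduled twitch measurement, ends at 6 hours or extubation, whichever is first. The definition also stops at extubation, so it closes just as the protocol's reason for calling recurrence harmless ceases to hold. Weakness after extubation is excluded even if sugammadex is then given for it.

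**Is the gap closed elsewhere?** No second adverse event definition appears. The relatedness grades do not widen the first. The list in Data variables has no stated cut-off for sugammadex dosing, so a late dose might appear in the data, but it would not be labelled an adverse event. The route for serious events is considered under the objection.

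**The case against.** The strongest reply has four parts.

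1. *A targeted definition is a legitimate choice.* Patients receive sugammadex whether or not they take part, and participants may receive less of it. The protocol names no added reaction risk from titration, so aiming the definition at recurrence is defensible. This has some force for the titration gap, but it bears on how a reaction is graded, not on whether it is recorded. It does not answer the second gap, which concerns recurrence itself.
2. *Serious events have a route.* The PI reviews them in real time, and they go to the IRB under institutional rules. This stands, and it limits the point. A reader might infer that a severe reaction or a reintubation would go unreported, or that a serious event must first meet the narrow adverse event wording. The documents support neither: the governing rules are not in them, and the second inference is only one possible reading of an undefined term. What remains is that the document does not define a serious adverse event and that a non-serious reaction is not an adverse event.
3. *Recurrence is unlikely.* Background argues that tight binding and renal clearance make it improbable once the ratio reaches 0.9. That is a reason to expect few events. It is also the proposition under study, so it cannot justify leaving later events out.
4. *Nothing inferential changes.* Agreed. The hypothesis ends at 6 hours or extubation, and no test uses adverse events.

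A reader might also try to size the defect by the time between the last scheduled twitch reading and extubation. That interval belongs to the measurement schedule. It would be the same under any adverse event definition, and the fix below adds no reading, so it is not used here.

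**Conclusion.** The point holds in limited form. The only adverse event definition in the document excludes non-serious reactions to the operating-room titration, and recurrent weakness or reintubation after extubation. The study could therefore report no adverse events although one of these had occurred. Recurrence that is detected and re-dosed before extubation is covered and is not in dispute.

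The consequence is confined to adverse-event reporting: no planned estimate, test or hypothesis is affected. An expected number of missed events cannot be given, because the documents state no sample size, reaction rate or recurrence rate. The conclusion rests on reading the definition literally and on planned titration being complete before the patient leaves the operating room, as Study design and Study procedures indicate. It does not rest on any claim that serious events would go unreported.

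**What to change.** In Data and safety monitoring:

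- Define an adverse event as any untoward event from the first study increment of sugammadex to a stated end point after extubation, which the sponsor sets and justifies. Name at least suspected reactions to sugammadex, and recurrent weakness or reintubation after extubation.
- Keep sugammadex given after leaving the operating room and before extubation as an event of special interest, tabulated separately.
- Grade every event with the three relatedness categories already in the section.
- Give or cite the definition of a serious adverse event that is used, and state that it does not depend on re-dosing.
- Drop the word standard, or apply it only to the relatedness categories.

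In Data variables, add the new event types and the times of leaving the operating room and of extubation, which are needed to place each event. The source already exists: "Data will either be recorded in real time by study assistants or retrieved from the electronic medical record".

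The cost is protocol wording and a modest extra review of the record, running past the point where study measurement now stops. Some events found will be due to surgery. With no comparator and no twitch reading scheduled after extubation, grading their relatedness will be uncertain, and the report should say so. No dose, measurement schedule or treatment rule changes.

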#### Statistical analysis:

Sample size is based on previous sugammadex dose-finding studies. The sample size in this study is similar to the largest previous sugammadex dose-finding studies. Descriptive statistics will be presented as number (%) for categorical variables or mean  $\pm$  standard deviation (SD) for continuous variables. Outcome variables (sugammadex dose) will be compared among twitch response groups using two-sample Student's *t* test with the assumption of unequal variance (Satterthwaite's degrees of freedom), ANOVA, two-sample test of proportions, Wilcoxon rank sum test and Pearson's Chi-squared test as appropriate. All P values will be 2-sided, and statistical significance will be defined as a P value of  $< 0.05$ . All statistical analyses will be performed with STATA 11.0 (Stata Corp LP, College Station, TX). Patient and procedure characteristics will be analyzed with R 4.2.1s (R Foundation for Statistical Computing, Vienna, Austria).

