**Background:**

Neuromuscular blocking drugs are used frequently during general anesthesia. The effects of neuromuscular blocking drugs are measured using a twitch monitor, that stimulates the ulnar nerve and measures the evoked response of the adductor pollicis muscle (thumb flexion), or other intrinsic hand muscle. When a series of 4 twitches is administered, the ratio of the first to the fourth twitch (train-of-four ratio) may be used to gauge the degree of muscle relaxation. A train-of-four ratio of 0.9 or greater is considered to represent adequate recovery from neuromuscular blockade. At the end of surgery, antagonists of neuromuscular blockade are commonly administered to reverse any remaining muscle relaxation. Sugammadex is a highly effective reversal agent of the aminosteroid neuromuscular blocking drugs rocuronium and vecuronium, which are the most commonly used neuromuscular blocking drugs. The dose-response relationship for sugammadex has never been completely determined. The dose of sugammadex depends upon the degree of neuromuscular blockade. When at least 1 twitch of the train-of-four is present, the recommended dose of sugammadex is 2 mg/kg. When there are no twitches of the train-of-four present, but at least 1 count of the post tetanic count is present, the recommended dose of sugammadex is 4 mg/kg. However, in several dose ranging studies of sugammadex, and in using sugammadex clinically, we and others have determined that smaller doses of sugammadex, often much less than 2 mg/kg, may be effective producing a train-of-four ratio of 0.9 or greater. Sugammadex binds (encapsulates) aminosteroid neuromuscular blocking drugs tightly and the sugammadex-aminosteroid complex is subsequently cleared by the kidney. Therefore we do not expect that recurrence of neuromuscular blockade would occur, even after small doses of sugammadex, as long as the dose of sugammadex is adequate to produce a train-of-four ratio of 0.9. Additional studies are needed to determine the dose-response for sugammadex and to confirm that recurrence of neuromuscular blockade does not occur after small doses of sugammadex. The purpose of the proposed study is to test the hypothesis that when sugammadex is titrated in 50 mg increments until the train-of-four ratio is 0.9 or greater, that this train-of-four ratio is maintained and there is no recurrence of neuromuscular blockade.

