**Objectives:**

The hypothesis is that when sugammadex is titrated in 50 mg increments until a train-of-four ratio of at least 0.9 is reached, that the train-four-ratio will remain at least 0.9 for 6 hours or until extubation, whichever comes first.

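### The trial's one stated hypothesis, that recovery is maintained without recurrence, has no analysis attached to it in the statistical section

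*Combined protocol and SAP*

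**What the plan says.** The Objectives section states the hypothesis that, after titration in 50 mg increments to a TOF ratio of at least 0.9, "the train-four-ratio will remain at least 0.9 for 6 hours or until extubation, whichever comes first". The Background section gives the same purpose: "that this train-of-four ratio is maintained and there is no recurrence of neuromuscular blockade". It also sets the wider need, to "determine the dose-response for sugammadex and to confirm that recurrence of neuromuscular blockade does not occur after small doses of sugammadex".

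The measurements follow from that. Under Study procedures, "Train-of-four ratio will be measured on arrival in the intensive care unit and then hourly for 6 hours or until extubation", and "If the train-of-four ratio is less than 0.9 at any time, additional sugammadex will be administered". Data variables lists "twitch monitoring data (prior to, during and after sugammadex administration" among the items recorded. Data and safety monitoring defines an adverse event as one that calls for sugammadex between leaving the operating room and extubation, for reporting to the IRB.

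The Statistical analysis section is the only statistical text. It says categorical variables will be summarised as number (%), and then: "Outcome variables (sugammadex dose) will be compared among twitch response groups". The tests listed are the unequal-variance t test, ANOVA, the rank-sum test, chi-squared and a comparison of two proportions. The section does not mention recurrence, maintenance of the ratio, the ICU readings or a confidence interval.

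**The concern.** The trial asks whether the ratio holds; the plan tests whether dose differs between groups. An analyst who follows the plan to the letter would produce P values about dose and, at most, a bare count for the question the trial was set up to answer.

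The likely result makes this serious. If no patient recurs, the report would show 0 (0%), and the Background's wish to confirm that recurrence does not occur invites the reader to take that as confirmation. A zero count in a modest cohort is compatible with a recurrence rate that is not negligible, and nothing in the plan would show the reader how large that rate could be.

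**Working it through.** **1. The hypothesis beside the analysis.**

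| Element | Hypothesis (Background, Objectives, Study procedures) | Statistical analysis section |
|---|---|---|
| Outcome | TOF ratio staying at or above 0.9 | Sugammadex dose |
| Population | One cohort, all titrated the same way (Study design) | Twitch response groups |
| Period | From reaching 0.9 to 6 hours or extubation | None stated |
| Inference | A recurrence rate in one group | Differences between groups |

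Two of the listed tests, the comparison of two proportions and chi-squared, suit binary data. Both still need groups to compare. Neither says how often the ratio fails to hold in a single cohort.

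**2. Figure to reproduce.** There is none. The supplied text gives no sample size, power, expected recurrence rate or acceptable limit; the sample size is justified by similarity to earlier dose-finding studies. The figures below therefore use assumed values of N.

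**3. What a zero count would show.** With 0 events in N patients, the exact (Clopper-Pearson) two-sided 95% upper limit is 1 − 0.025^(1/N). If the true rate is p, the chance of seeing no event is (1 − p)^N.

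| Assumed N | Upper limit with 0 events | Chance of 0 events if p = 2% | Chance of 0 events if p = 5% |
|---|---|---|---|
| 20 | 1 − 0.025^(1/20) = 16.8% | 0.98^20 = 66.8% | 0.95^20 = 35.8% |
| 50 | 1 − 0.025^(1/50) = 7.1% | 0.98^50 = 36.4% | 0.95^50 = 7.7% |
| 100 | 1 − 0.025^(1/100) = 3.6% | 0.98^100 = 13.3% | 0.95^100 = 0.6% |

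The rates of 2% and 5% are also assumptions. With 50 patients and a true rate of 2%, the trial would see no recurrence more than one time in three.

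**4. The same calculation reversed.** The N at which zero events brings the upper limit down to p is ln(0.025)/ln(1 − p), rounded up: 36 for 10%, 72 for 5%, 183 for 2% and 368 for 1%.

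None of the listed comparisons yields these limits. A one-sample proportion with an exact interval does.

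**The case against.** The strongest reply is that little is really missing. The threshold, period and reading schedule are fixed in Objectives and Study procedures, the readings are recorded, the number (%) sentence would cover a count of patients with recurrence, and an interval can be added later from the same data. The dose analysis also has a purpose, since the Background says the dose-response still needs to be determined. All of this is correct. It limits the repair to the statistical section and justifies keeping the dose comparisons. It does not give the hypothesis a named endpoint or an inference, and a general descriptive sentence that does not mention recurrence commits no one to an interval.

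A reader might go further and infer that the plan leaves open whether a patient brought back to 0.9 by more sugammadex counts as a recurrence, so that a cohort with low readings could be reported as having none by looking only at the last reading. The documents do not support that. A patient who falls below 0.9 has not remained at 0.9, which is what the Objectives require. Anticipated risks treats the fall itself as the recurrence and re-dosing as the response: "If there is any recurrence of neuromuscular blockade, this will be detected by twitch monitoring and additional sugammadex will be administered". The adverse event definition likewise counts re-dosing after the operating room, whatever the later readings. The statistical section does not formally say whether patients or readings are counted, but a hypothesis about remaining above a threshold points to patients.

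**Conclusion.** The point holds. The only stated hypothesis has no named endpoint and no inference in the statistical section; the inference that is planned concerns dose. This rests on the text alone and needs no assumption.

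Its numerical size cannot be fixed, because N is not in the supplied text. The upper limits of 16.8%, 7.1% and 3.6% are a general property of zero-event data at assumed sizes of 20, 50 and 100, not measured errors in this plan. They show why a bare zero should not be reported as absence of recurrence.

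The point does not extend to data collection, which is adequate for the endpoint, or to re-dosed patients, whom the documents already indicate should count. The endpoint and its interval should be written down before results are known, because the trial's main conclusion depends on them.

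**What to change.** In the Statistical analysis section:

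- Name as primary endpoint the per-patient proportion with any recorded TOF ratio below 0.9, scheduled or unscheduled, after first reaching at least 0.9 and up to 6 hours in the ICU or extubation. Limiting events to the scheduled ICU readings would miss falls before ICU arrival and unscheduled low readings, both of which the hypothesis covers.
- Count a patient as an event at the first such reading, regardless of any later additional sugammadex. This agrees with Objectives, Study procedures, Anticipated risks and the adverse event definition.
- Report the proportion with an exact (Clopper-Pearson) 95% confidence interval, and word the conclusion as the recurrence rate excluded by the upper limit.
- Keep the dose comparisons as a secondary analysis serving the dose-response aim in the Background.

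The cost is a few sentences, one extra calculation on data already being recorded, and a more cautious conclusion. Conduct and sample size do not change.
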